8	Fluids	
 
All patients commenced on IV Hartmann's solution within one hour of admission to the emergency department by a clinician and at an initial rate of 5-10 ml /kg in response to hypovolemia until resuscitation goals reached.
 
Then a rate of 1-2 ml/kg/hour for patients not tolerating PO in the first 48 hours.
 
	IAP	IV fluids N / Y Time commenced from admission What initial fluid was given? Initial prescribed rate Initial received rate Average rate 2 nd 24 hours Average rate 3 rd 24 hours Fluid bolus given (# times and and timing) Volume / 24 hours over 72 hours?
9	Anticoagulation	All patients with predicted severe AP considered for or started on anticoagulation within 24 hours of admission	-	Anticoagulation N / Y Medication prescribed When started (hours from admission)
10	Antibiotics	Antibiotic prophylaxis not recommended for the prevention of infectious complications in AP	IAP	Antibiotic N / Y Antibiotic indication

11	Nutrition	
 
1. No patients made 'nil-by-mouth' and no food withheld unless there was a clear reason.
 
2. Offer EN to anyone with MSAP or SAP starting within 72 hrs.
 
3. PN avoided unless EN fails or is contraindicated
 
	NICE	Initial NBM N / Y From admission given trial of light diet. N / Y Initial NG or NJ? EN started within 72 hours if needed N / Y EN prescribed rate PN started if EN was not tolerated or contraindicated.
12	ERCP/ES	ERCP is indicated in patients with biliary pancreatitis and acute cholangitis within 48 hours of admission.	IAP	ERCP N / Y Indication: cholangitis or cholestasis When done? (hours)

\* Reference of guideline from which the QPI is primarily taken from

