Type of opioid prescribed (if any)	Codeine/ Morphine/ Fentanyl/ Tramadol/ Oxycodone/ Other (please specify)/ no opioids prescribed
Date opioid analgesia first administered	Date (dd/mm/yyyy)
Time opioid medication is administered to patient	24 hour clock
Route	PO/ IV
(If regular) daily dose	mg
(If PRN) total dose in first 72 hours	mg

(If yes) Date opioids first administered	Date (dd/mm/yyyy)
(If yes) Time opioid medication first administered as per drug chart?	24 hour clock
Further analgesic modalities	PCA/ ketamine/ local nerve blocks/ other (please specify)
Transfer to different hospital	
Patients with predicted severe disease discussed with specialised pancreas service ( Appendix B ) in first 72 hours from admission	Yes/ No/ not applicable
Patient transferred to a different hospital in the first 72 hours?	Yes/No
(If yes) Date of transfer	Yes/No
(If yes) Location transferred to	List of hospitals
(If yes) Reason for transfer to different hospital?	Severe disease/ requires ERCP/ requires interventional management of local complication/ other (free text)
ERCP	
Cholangitis in first 72 hours ( Appendix F )	Yes/ No
Cholestasis in first 72 hours (radiological + deranged LFTs)	Yes/ No
ERCP performed in the first 72 hours	Yes/ No
Fluid management*	
Baseline variables	
Bag 1	
Date of administration	Date (dd/mm/yyyy)
Time of administration	Time (24-hour)
Volume administered	Volume (ml)
How long does fluid run for?	Time (hours)
Type of fluid	0.9% Normal saline/ Hartmann's/ plasmalyte/ colloid/ 0.45 saline + dextrose/ 0.18 saline + dextrose/ other (please specify)
Further administration of intravenous fluid (IVF) in the first 3 days of admission? ( Appendix B )	Yes/no
Bag 2	
Date of administration	Date (dd/mm/yyyy)
Time of administration	Time (24-hour)

Volume administered	Volume (ml)
Time fluid is administered	Time (hours)
Type of fluid	0.9% Normal saline/ Hartmann's/ plasmalyte/ colloid/ other (please specify)
Further administration of intravenous fluid (IVF) in the first 2 days of admission?	Yes/no
Documented fluid review after 12 hours ( $\pm$ 4 hours)	Yes/no
Documented fluid review after 24 hours ( $\pm$ 4 hours)	Yes/no
Documented fluid review after 48 hours ( $\pm$ 4 hours)	Yes/no
Documented fluid review after 72 hours ( $\pm$ 4 hours)	Yes/no
Early Nutritional support	
On admission patient kept nil by mouth (NBM)	Yes/no

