Date of mortality (within 30 days of first admission)	Date (dd/mm/yyyy)/ not dead
Date of discharge	Date (dd/mm/yyyy)/ not discharged

*\* Fluid therapy data collection guide: If collaborators respond, 'yes' to the question 'further administration of IVF in first 72 hours of admission?' a further set of questions will arise for 'bag 2', 'bag 3' etc.*

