## 6. Ethical and regulatory considerations

### 6.1 Ethical considerations

This study will take the form of a prospective cohort study. There will be no change to the management of patients, no advice or guidelines given to the data collectors/clinical team. The aim will be to collect information on the routine practice of different hospitals around AoNZ. There is no foreseen impact on standard patient care and therefore no risk to patients involved in this study. There will be no contact with patients and follow-up data will be collected from routine clinical notes; No phone calls will be made.

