## 8. Statistical analysis

The study will be reported in accordance with the Strengthening the Reporting of Observational Studies in Epidemiology (STROBE) statement (21). The primary analyses will be descriptive assessments of adherence to unambiguous recommendation in the selected domains of early AP management. Descriptive analysis will be performed where normal continuous variables will be compared via student's t test, and non-normal continuous variables will be compared via Mann-Whitney U test; if >2 categories a one-way ANOVA or Kruskal-Wallis test will be used for normal and non-normal variables respectively, Chi-square tests will be used to detect differences between categorical variables. All analyses will be conducted under a two-tailed hypothesis. Multiple imputation may be used in the case of missing data.

Secondary analyses will evaluate the differences in results according to the hospital. Risk-adjusted funnel plots will be produced to test the performance of individual, anonymised centres for normal rates of primary and selected secondary outcomes. Funnel plots' Y-axes will demonstrate QPI of a management domain and X-axis will show the number of patients admitted in each hospital. Furthermore, differences in clinical outcomes between patients that are managed according to best available evidence (QPI) and those that were not will be explored through mixed effects multivariable logistic models. These models will use the patient at the fixed effect level 1 and the hospital as the random effect level 2 (using the R lmer package) will be performed. A one level, fixed effect binary logistic regression model using a pooled dataset from 5 multiply imputed datasets will also be used in the event of substantial missing data.

Variable selection will be based on statistically significant univariable analysis and those variables deemed clinically significant. Fixed, forced entry will be used to adjust the main outcome measure, The effect of interaction, and sequential removal of non-significant variables will be assessed using changes in Akaike information criteria for multilevel models, and p-values for multiple imputed fixed models.

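### The initial fluid rate in QPI 8 part 1 has no time unit and depends on hypovolaemia and goals that are neither defined nor collected, so it cannot be scored

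*Protocol*

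**What the plan says.** The fluid indicator is row 8 of Table 1 in Protocol section 3. Part 1 opens "All patients commenced on IV Hartmann's solution within one hour of admission to the emergency department by a clinician" and continues "at an initial rate of 5-10 ml /kg in response to hypovolemia until resuscitation goals reached". Part 2 follows: "Then a rate of 1-2 ml/kg/hour for patients not tolerating PO in the first 48 hours".

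Section 5.5 records body weight and, for each bag, the date, time, volume, running time and type of fluid. The only item near an assessment of response is a yes/no for a documented fluid review at 12, 24, 48 and 72 hours (for example "Documented fluid review after 24 hours").

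Section 8 sets the standard that the indicators must meet: "The primary analyses will be descriptive assessments of adherence to unambiguous recommendation in the selected domains of early AP management". Fluid compliance feeds the overall compliance outcome in section 4.1, the between-hospital comparison by domain in section 4.2 and the funnel plots in section 8.

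**The concern.** Three things are unsettled in part 1.

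- **Unit.** A rate needs a time base. Part 2 gives one in the same cell; part 1 does not. Per hour is the likely intent, but the text would also bear a reading as a volume per kilogram.
- **Who must receive it.** The sentence begins with all patients, then makes the rate a response to hypovolaemia. Appendix B does not define hypovolaemia, and section 5.5 has no field for it.
- **When it ends.** The rate stops at resuscitation goals, and part 2 takes over from there. The goals are not defined and their attainment is not recorded.

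For a patient given Hartmann's on time, the fluid classification can therefore turn on the scorer's reading. If readings differ between sites or scorers, part of the apparent hospital variation in the fluid funnel plot would come from scoring rather than care. A later SAP could supply the unit, but it could not recover volume status that was never collected.

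**Working it through.** The plan has no figure of its own to reproduce here. The check has two parts: what the form collects, and whether the open points change a patient's score.

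**What the rule needs against what is collected**

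| Needed to score the part 1 rate | In section 5.5 or the appendices available? |
|---|---|
| Weight, bag volume, running time | Yes |
| Fluid type and start time | Yes |
| Time unit of the threshold | Not stated |
| Hypovolaemia at presentation | No definition and no field; no heart rate, blood pressure, urine output, haematocrit, urea or lactate |
| Resuscitation goals and time met | No definition and no field; only whether a fluid review was documented |

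Appendix A gives urine-output limits under the RIFLE criteria, but these serve only a yes/no for acute renal failure over the 30-day follow-up.

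**Does the missing unit change the score?**

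Inputs: the 5-10 threshold from part 1 and the 1-2 ml/kg/hour range from part 2. Weights of 60-100 kg and the bag sizes and running times are assumptions.

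- Volume reading: ml/kg = volume / weight
- Hourly reading: ml/kg/h = volume / (weight × hours)

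| First bag | Weight | ml/kg | Volume reading | ml/kg/h | Hourly reading |
|---|---|---|---|---|---|
| 500 ml over 4 h | 60 kg | 500/60 = 8.33 | pass | 8.33/4 = 2.08 | fail |
| | 80 kg | 500/80 = 6.25 | pass | 6.25/4 = 1.56 | fail |
| | 100 kg | 500/100 = 5.00 | pass | 5.00/4 = 1.25 | fail |
| 1,000 ml over 2 h | 60 kg | 1000/60 = 16.67 | fail | 16.67/2 = 8.33 | pass |
| | 80 kg | 1000/80 = 12.50 | fail | 12.50/2 = 6.25 | pass |
| | 100 kg | 1000/100 = 10.00 | pass | 10.00/2 = 5.00 | pass |

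The first bag changes class at every weight in the range, and the second changes class in the opposite direction at weights below 100 kg.

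**Does the condition change the score once the unit is fixed per hour?**

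Take 1,000 ml over 8 hours, which is 125 ml/h:

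- 60 kg: 125/60 = 2.08 ml/kg/h, just above the part 2 range
- 70 kg: 125/70 = 1.79 ml/kg/h
- 80 kg: 125/80 = 1.56 ml/kg/h
- 100 kg: 125/100 = 1.25 ml/kg/h

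All four fall short of 5 ml/kg/h, so a hypovolaemic patient fails part 1. From 70 to 100 kg the same bag lies within 1-2 ml/kg/h, so it meets the part 2 rate if the patient was not hypovolaemic. The recorded data are identical in the two cases.

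**A related slip.** The bag 2 question reads "Further administration of intravenous fluid (IVF) in the first 2 days of admission", whereas the data collection guide under the table reads "further administration of IVF in first 72 hours of admission". The bag 1 question says 3 days, in line with the guide. Taken literally, the bag 2 label would end fluid capture a day early.

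**The case against.** The strongest reply is that the missing unit is an editorial gap. The text calls the figure a rate, part 2 continues in ml/kg/hour, and the Table 1 metrics list bolus separately from rate. On that view few scorers would take 5-10 ml/kg as a volume, and a SAP could settle it. This largely stands for the unit, and the hourly reading is the more natural one. It does not help with the condition, where the last example flips with the unit already fixed.

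The sentence can also be read sensibly: everyone starts Hartmann's, and only hypovolaemic patients need the rate. That is a fair reading, but it cannot be applied without knowing who was hypovolaemic.

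Section 8 might be taken as a filter that drops ambiguous elements. It does not say that this element is dropped, and Table 1 still lists it as part of the indicator.

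Part 2 applies only to patients not tolerating oral intake, so a normovolaemic patient on 1,000 ml over 8 hours is not automatically under part 2. This is correct. The example shows only that the part 2 rate is met, and whether the part 1 rate applied remains unknown.

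Appendix D is cited in section 3 but is not in the text available and might contain a unit or definition. It is described as a guideline table, so it would not add a field to section 5.5.

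Finally, the charts are assumed and only one element of one of twelve indicators is affected. Both points stand and limit the size of the finding.

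**Conclusion.** The concern holds. As written, compliance with the part 1 rate cannot be determined from the data that the protocol collects, nor can the moment at which part 2 takes over. The rate therefore does not meet section 8's own requirement that recommendations be unambiguous. Fluid type, the one-hour start and most of part 2 are unaffected.

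The effect on the overall compliance proportion cannot be computed: the documents give neither the share of hypovolaemic patients nor the distribution of bag rates. The examples show that single patients change class; they do not show how many. This is a real defect in one of twelve domains that should be corrected before scoring, and it does not invalidate the study. The conclusion rests on section 5.5 and the appendices available, without Appendix D.

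**What to change.** **Preferred change**

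1. State the rate as 5-10 ml/kg/hour, or replace it with a bolus volume and a time limit.
2. Say that Hartmann's and the one-hour start apply to all patients, and the rate only to those with hypovolaemia.
3. Have the Scientific Advisory Group set a chart-based definition of hypovolaemia, for example as recorded in the first-review note, or heart rate or blood pressure beyond stated limits.
4. Add to section 5.5 a field for hypovolaemia at first review (yes / no / not documented) and, where documented, the date and time goals were met.
5. Change the bag 2 label to 72 hours.

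**Fallback if those data cannot be collected**

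From part 1, score fluid type and start time only. Report ml/kg/h descriptively from bag volume, running time and weight, and leave the part 1 rate out of the overall score.

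**Cost**

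The preferred change rewords one table row, corrects one label and adds two chart-review items. Its weakness is that, by section 6.1, "follow-up data will be collected from routine clinical notes", with no patient contact, so volume status and goal time will be undocumented in some charts; the third response category makes that visible. The fallback needs no new field and remains available after data collection has closed.

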## 3. Quality Performance Indicators

Multiple practice guidelines have been published for the management of AP (14–19). The recommendations in these guidelines are usually based on a systematic review of the relevant literature and the evidence on which is based on the available evidence, which is usually graded. Quality performance indicators will be drawn from these evidence-based recommendations for each of the nominated management domains that are relevant to the management of patients within the first 72 hours from admission to hospital. Any differences in the recommendations between the source guidelines will be resolved by discussion amongst the Scientific Advisory Group and consensus established for the QPIs.

The QPIs were developed for the following management domains: (Appendix D: Table 1 with guidelines)

**Table 1.** Quality Performance Indicators

	Domain	QPI	Ref*	Metrics
1	Diagnosis	All patients diagnosed within 12 hours of admission	IAP	RAC criteria for diagnosis: enzymes 3xUL, typical pain ± CT scan
2	Aetiology	All patients had tests for aetiology determined within 24 hours of admission	IAP	U/S for gallstones ETOH history with intake (units per week, timing of binge to pain) If both negative then lipids, IgG4, drugs
3	Severity (predicted)	All patients had prediction of severity on admission	IAP	N / Y, if yes method (drop-down of all options and other) Further drop-down bar will the give options for severity (mild, moderate, and severe)

4	Severity (actual)	All patients had actual severity determined at 48 hours	-	N / Y, if yes method (drop-down RAC, DBC and other) Further drop-down bar will the give options for severity (mild, moderate, and severe)
5	CT scan	Initial CT assessment performed after 72-96 hours if poor response to initial management or clinical deterioration, unless there is diagnostic uncertainty. Not required for severity prediction.	IAP	N / Y, if yes indication (drop-down with other)
6	Transfer	All patients with predicted or actual severe AP in the first 72 hours are discussed with specialist pancreas service.	Nice	N / Y Indication for transfer (drop-down)
7	Analgesia	All patients given narcotic analgesia within one hour of admission	-	Step-up or step-down approach? IV analgesia given on admission N / Y NSAIDS given to mild AP Analgesics prescribed

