## 4. Outcomes

### 4.1. Primary outcomes

- Proportion of patients that were managed in compliance with quality performance indicators overall

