### 4.2. Secondary outcomes

- Variation in compliance with QPIs between hospitals for each of the management domains
- Requirement for mechanical ventilation (invasive and non-invasive)
- Requirement for renal replacement therapy
- Requirement for inotropic or vasopressor support
- Intervention for a complication of AP
- Alive and discharged at 30-days

[figure not shown]

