## 5.5. Required data

Demographic details	
Age	Year of birth
Sex	Male/ Female/ Other
Ethnicity	European/ Pasifika/ Maori/ Asian/ Middle-Eastern/ Latin American/ African (MELAA)/ other ethnicity
Postcode	
Weight	kg
Height	cm
Smoking history	Current smoker /previous smoker /never smoker e-cigarette /cigarette
Admission details	
Date of first review by doctor/prescriber	Date (dd/mm/yyyy)  *From ED admission note
Time of first review by doctor/prescriber – as per admission note	24 hour clock time
Pancreatic enzymes at admission	Lipase/ Amylase/ Pancreatic amylase (tick one or more and give admission level and indicate what 3x upper limit is
Lipase/ amylase/ pancreatic amylase level	U/L
Epigastric pain confirmed on admission note	Yes/Non-epigastric abdominal pain/ No abdominal pain
Confirmation of AP diagnosis with imaging as per radiological report	MRI/ CT/ Abdominal USS
Charlson Comorbidity Index ( Appendix E )	Score out of 37
Aetiology	
Significant ETOH history investigated in first 72 hours	Yes - from medical history, Yes - ETOH blood test, No

Hypertriglyceridemia investigated in first 72 hours	Yes/No
Acute pancreatitis severity	
Predicted severity on admission as documented in clinical notes (72 hours)	Mild/ moderately severe/ severe
Method used to predict severity	Modified Glasgow/ Ransons'/ BISAP/ APACHE II/ SIRS/ CRP (>150)/ Other (please specify)/ Clinical judgement (no prediction tool)/ No prediction made.
Imaging	
CT assessment performed in the first 72 hours of presentation	Yes/ No
Indication for CT prior to 72 hours	Diagnostic uncertainty/ confirmation of severity based on clinical predictors of severe AP/ Failure to respond to conservative treatment or in the setting of clinical deterioration/ other (please specify)
Imaging of the gallbladder during admission	USS/ CT (gallstones seen on CT)/ MRI/ EUS/ prior imaging confirming gallstones/ previous cholecystectomy/ no imaging
Antibiotics	
Antibiotics administered in first 72 hours of presentation	Yes/ No
Indication for antibiotics	Cholangitis concomitant extrapancreatic infection/ prophylactic/ other – please state
Analgesia	
Simple analgesia (paracetamol/ NSAIDs) prescribed	Paracetamol/ NSAIDs/ Not charted
Simple analgesia frequency	regular/ PRN
Date simple analgesia first administered	Date (dd/mm/yyyy)

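### Eligibility for QPI 9 and for the predicted limb of QPI 6 depends on whether the treating team wrote down a severe prediction, so documentation habits can distort hospital comparisons in these two domains, in either direction.

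*Protocol*

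**What the plan says.** Three indicators in Table 1 (Protocol, Section 3) are linked.

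- QPI 3 applies to everyone: "All patients had prediction of severity on admission".
- QPI 6 (Transfer): "All patients with predicted or actual severe AP in the first 72 hours are discussed with specialist pancreas service".
- QPI 9 (Anticoagulation): "All patients with predicted severe AP considered for or started on anticoagulation within 24 hours of admission". It has no actual-severe limb.

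In Section 5.5 the only source of predicted severity is the field labelled "Predicted severity on admission as documented in clinical notes (72 hours", graded mild, moderately severe or severe. The method field lists six named tools (Modified Glasgow, Ranson's, BISAP, APACHE II, SIRS and CRP above 150) and a free-text other option, and ends with "Clinical judgement (no prediction tool)/ No prediction made". The field that serves QPI 6 reads "Patients with predicted severe disease discussed with specialised pancreas service" in the first 72 hours, answered yes, no or not applicable.

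Section 4.2 names as a secondary outcome "Variation in compliance with QPIs between hospitals for each of the management domains". Section 2 also plans to relate compliance in each domain to clinical outcomes, and Section 8 plans risk-adjusted funnel plots by hospital.

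**The concern.** The result of one indicator decides who is counted in another. A patient with no recorded prediction fails QPI 3 and then cannot be recognised as belonging to QPI 9 or to the predicted limb of QPI 6. Two hospitals giving the same care could report different compliance on anticoagulation and referral because one writes predictions down for everyone and the other only for some. Where predictions are recorded, they may rest on different tools or on unaided judgement, so predicted severe is not one standard across sites.

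At stake are the hospital comparisons in these two domains and the planned link between compliance in each domain and outcome. A difference in note-keeping could be read as a difference in treatment or referral.

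**Working it through.** **What the plan gives.** The protocol states no expected compliance, number of eligible patients or documentation rate, so it has no figure to reproduce. The check has two parts: tracing the denominators, and an illustration on assumed inputs.

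**1. Can the prediction be rebuilt from the form?** No. The only laboratory levels in Section 5.5 are pancreatic enzymes. It has no admission temperature, pulse, respiratory rate, white cell count, urea or CRP value. CRP above 150 is itself a listed method, yet no CRP value is recorded. The absence of a prediction is a valid answer rather than a missing value, and the form lacks the inputs to impute one.

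**2. Does the actual-severe limb of QPI 6 help?** As written in Table 1, yes. On the form, hardly: the only discussion field is worded for predicted severe disease, so a patient with no prediction who becomes severe has no clear place in it.

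**3. Size and direction.** Notation, per 100 admissions:

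- S = patients who would be predicted severe on a common standard. Assumed 20, an upper illustration taken from the 20% with moderate or severe disease in Section 1.
- d = share of them with a documented severe prediction. Assumed 40% or 70%.
- t = true QPI 9 compliance among all S. Assumed 50% or 60%.
- RR = treatment rate in documented relative to undocumented patients. Assumed 0.5, 1 or 2.

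Since t = d·a + (1 − d)·b and a = RR·b, compliance is b = t / (d·RR + 1 − d) in the undocumented and a = RR·b in the documented.

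For t = 60%, d = 40%, RR = 2: b = 0.60 / (0.80 + 0.60) = 0.429 and a = 0.857. For RR = 0.5: b = 0.60 / (0.20 + 0.60) = 0.75 and a = 0.375.

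If patients without a documented severe prediction are excluded, the reported figure is a. If they count as compliant, it is [(100 − S) + S(1 − d) + S·d·a] / 100. For t = 60%, d = 40%, RR = 2 the latter is (80 + 12 + 8 × 0.857) / 100 = 98.9%, against (80 + 12) / 100 = 92% under full documentation.

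| t | d | Excluded: RR 0.5 / 1 / 2 | Counted compliant: RR 0.5 / 1 / 2 | Counted compliant, full documentation |
|---|---|---|---|---|
| 60% | 40% | 38 / 60 / 86% | 95.0 / 96.8 / 98.9% | 92% |
| 60% | 70% | 46 / 60 / 71% | 92.5 / 94.4 / 95.9% | 92% |
| 50% | 40% | 31 / 50 / 71% | 94.5 / 96.0 / 97.7% | 90% |
| 50% | 70% | 38 / 50 / 59% | 91.4 / 93.0 / 94.2% | 90% |

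The excluded column does not depend on S. With S = 10, t = 60%, d = 40%, the counted-compliant figures are 97.5 / 98.4 / 99.4% against 96%.

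**4. Precision.** The normal-approximation half-width at 60% is 1.96 × √(0.24 / n), which is rough at these sizes. For n = 20 it is 21 points, and for n = 8 (that is, 20 × 0.40) it is 34 points. Section 8 puts all admitted patients on the funnel plot's horizontal axis. If the limits were also built on that count, n = 100 would give about 10 points.

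**5. Overall score.** The primary outcome is "Proportion of patients that were managed in compliance with quality performance indicators overall". If it is all-or-nothing, a patient who fails QPI 3 has already failed, so nothing is gained. If it averages items, and the nine QPIs other than 3, 6 and 9 all apply and are met, a patient who would fail both 6 and 9 scores 10/12 = 83% if documented and 9/10 = 90% if not. One who would meet both goes from 12/12 = 100% to 9/10 = 90%.

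**The case against.** A reader might infer that under-documenting hospitals will look better, that the ranking of hospitals reverses, or that the plan rewards failing QPI 3. The documents do not support this. Nothing in them links documentation to treatment, and with undocumented patients excluded the reported figure can rise, stay or fall. Hospitals with the same true rate that report different figures show distortion, but there is no true order to reverse. A hospital that documents no severe prediction has no QPI 9 result, which is not a good one.

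Four further points on the other side:

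- **Scoring of indicators that do not apply may sit in a statistical analysis plan that is not at hand.** This stands: the missing scoring rule is not the finding. Such a plan cannot, however, supply admission values or answers that the form never collected.
- **QPI 3 is its own domain, so under-documentation is visible there.** This stands, and the share without a prediction comes from an existing field. It signals the problem without correcting QPIs 6 and 9.
- **Testing whether clinicians act on their own prediction is a legitimate construct for a study of routine practice.** This stands, and is why the documented version should be kept beside a common one. It does not make the documented version comparable between hospitals that use different tools.
- **A check in actual severe disease is possible for QPI 9 without new fields.** This largely stands: the anticoagulation fields are not restricted to predicted-severe patients, and persistent organ failure can be approximated from fields on the form.

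**Conclusion.** The point holds as a risk of distortion whose direction is unknown. What rests on the text alone is that eligibility for QPI 9 and for the predicted limb of QPI 6 follows from a documented prediction, that the form cannot rebuild that prediction, and that the discussion field is narrower than QPI 6. The size rests on assumed inputs. A true 60% could be reported as anything from 38% to 86% when 40% of eligible patients are documented and the others are excluded. Under-documentation raised the figure in every scenario run if non-applicable patients count as compliant. Fewer identifiable patients also cost precision, whatever the direction.

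The harm falls on the hospital comparisons in these two domains and on the analyses relating them to outcome. An all-or-nothing primary score would gain nothing from it. The change is cheap and should be made. It concerns measurement only and takes no view on the clinical content of the indicators.

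**What to change.** 1. Reword the discussion field in Section 5.5 so that discussion with the specialist service is recorded for every patient regardless of prediction. This matches QPI 6 as written.
2. Add to Section 5.5 the admission components of one score already listed on the form, chosen by the Scientific Advisory Group. Assign predicted severity from them centrally, and report QPI 9 and the predicted limb of QPI 6 on that common denominator alongside the documented-prediction version. Keep the documented prediction for scoring QPI 3.
3. If no items are added, report QPIs 6 and 9 also in patients with actual severe disease, derived from the organ-failure fields and Appendix A, and show each hospital's share without a prediction. Those fields cover 30 days and carry no onset dates, so they match the 72-hour window of QPI 6 only approximately.

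Do not use bounds that count every unpredicted patient as a failure. Section 1 implies that about 80% of patients have mild disease (100% − 20%). With assumed figures of 4 of 5 documented patients treated and 40 unpredicted, the bounds would run from 4/5 = 80% down to 4/45 = 9%, which says little.

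The cost is a slightly longer form, some missing values in the added items, and a short protocol edit. Step 3 needs no new fields for QPI 9. For QPI 6 it depends on step 1.

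### Anticoagulation and nutrition indicators (QPIs 9 and 11) count actions and reasons that the Section 5.5 data list does not record

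*Protocol*

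**What the plan says.** Section 3, Table 1, sets out twelve quality performance indicators, each with a Metrics column.

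- **QPI 9 (anticoagulation).** Patients with predicted severe disease comply if "considered for or started on anticoagulation within 24 hours of admission". The metrics are given or not, which drug, and hours from admission to start.
- **QPI 11 (nutrition), part 1.** No nil-by-mouth (NBM) order and "no food withheld unless there was a clear reason". One metric is "From admission given trial of light diet. N / Y".
- **QPI 11, part 2.** "Offer EN to anyone with MSAP or SAP starting within 72 hrs". The metric is "EN started within 72 hours if needed N / Y".
- **QPI 11, part 3.** "PN avoided unless EN fails or is contraindicated". The metric is "PN started if EN was not tolerated or contraindicated".

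Section 5.5 lists the data to be collected. For anticoagulation it asks about regular therapy before admission and its continuation. A further item on regular anticoagulation has 24-hour and 48-hour options, and a separate item gives the agent newly commenced, with options for not started and free-text other. For nutrition it asks about NBM on admission with its indication, tolerance of clear fluids by 24, 48 and 72 hours, EN started, tolerated, route and rate, and PN given and its rate.

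Section 8 uses compliance in three ways: as the descriptive primary result, as the vertical axis of the hospital funnel plots by domain, and as the exposure in the mixed-effects outcome models.

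**The concern.** An indicator can be scored only if the data separate those who met it from those who did not. QPI 9 and QPI 11 part 2 each allow compliance through an act that leaves no trace in either list: deciding against anticoagulation after weighing it, or offering EN that the patient declines. QPI 11 parts 1 and 3 depend on facts that Table 1 names but Section 5.5 does not carry over.

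The result would be misclassified compliance in these two domains, feeding all three uses in Section 8. An analysis plan can set scoring rules, but it cannot supply a field that was never collected. The Study Timeline has the form finalised on 27 March 2024 and REDCap closed to new entries on 30 September 2024. Section 5.3 has the local data copies destroyed after upload, leaving only the key that links REDCap numbers to patients. Recovery would mean going back to the charts.

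**Working it through.** The protocol gives no figure to reproduce. The check sets each indicator beside the two lists.

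| What the indicator turns on | Table 1 Metrics | Section 5.5 |
|---|---|---|
| QPI 9: considered | no item | no item (free-text other only) |
| QPI 9: started | yes | yes, by agent |
| QPI 9: within 24 h | hours to start | no time for new anticoagulation; 24 h/48 h options belong to the regular-therapy item |
| QPI 11.1: NBM and reason | NBM yes/no | NBM on admission, with indication |
| QPI 11.1: food withheld | trial of light diet | no item; clear fluids only |
| QPI 11.2: EN offered | no item; started only | no item; started only |
| QPI 11.3: EN failed | not tolerated | EN tolerated yes/no |
| QPI 11.3: EN contraindicated | contraindicated | no item; PN yes/no and rate |

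**Which patients share a record if Section 5.5 is followed**

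1. Anticoagulation considered and withheld for a reason, and never considered: both are not started, unless someone uses the free-text option.
2. New anticoagulation at 10 hours and at 40 hours: the same agent entry, with no time.
3. EN offered and declined, and never offered: both are EN not started.
4. Kept on clear fluids with no NBM order on admission, and given food: both can show no NBM and clear fluids tolerated. An NBM order made later can show only as clear fluids not tolerated, without a reason.
5. PN because EN was contraindicated, and avoidable PN: both are PN yes, EN not started.

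**Counts.** Of the two acts, considering and offering, 0 of 2 have an item in either list. Row 11 has six metrics. Four have a Section 5.5 item (NBM, NG or NJ route, EN started, EN rate), one has none (light diet), and one is partly covered (PN and EN tolerance, but not contraindication): 4 + 1 + 1 = 6.

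**Reach of QPI 11 part 2.** Section 1 puts moderate or severe disease at 20%. Let s be the share of these patients who started EN. The share of the cohort whose part 2 status is open is 0.20 × (1 − s), which is 0.20 at s = 0 and 0.10 at s = 0.5. The 20% is a background figure, not an estimate for this cohort. The protocol gives no share for predicted severe disease, so the reach of QPI 9 cannot be stated.

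**Illustration, on assumed inputs.** If 10% to 50% of moderate or severe patients were offered EN but did not start, scoring on starting lowers part 2 compliance by 10 to 50 points among them. That is 0.20 × 0.10 = 0.02 to 0.20 × 0.50 = 0.10 of the cohort. If 10% to 30% of predicted severe patients were considered but not started, QPI 9 falls by 10 to 30 points in that group. Missed withholding of food acts the other way on part 1, so no net direction follows.

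**The case against.** The strongest reply is that the Metrics column already fixes the measurement: it scores starting, an observable act. Section 6.1 rules out patient contact and relies on routine notes, where a consideration or a declined offer may go unwritten. A new field could then measure charting habits, which may differ between hospitals. This stands as a reason to allow a second remedy, rewording the indicators. It does not remove the mismatch, because the indicators as written still credit considering and offering. The protocol also collects a similar act elsewhere: "Patients with predicted severe disease discussed with specialised pancreas service" is a Section 5.5 item for QPI 6.

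Second, the REDCap form is not shown and may follow Table 1. This stands for light diet, the reason for PN and the anticoagulation start time, where the finding is only that two parts of the protocol disagree. It does not help for considering and offering, which are in neither list.

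Third, a reader might infer that exactly two of twelve domains, or 17%, are affected. The documents do not support that as an extent, because only these two were checked. QPI 12, for example, asks for hours to ERCP, while Section 5.5 records only whether ERCP took place within 72 hours.

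Fourth, a reader might make a separate finding of the contrast between EN for all moderate or severe patients and the metric's limit to those who need it. Whether patients who are eating enter the denominator is a scoring rule that an analysis plan can settle.

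**Conclusion.** The concern holds in a limited form. Two acts that count as compliance are collected nowhere in the protocol. Section 5.5 also lacks three things that Table 1 lists: time to start of new anticoagulation, trial of light diet, and EN contraindication as the reason for PN.

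A reader might infer that compliance in both domains is misclassified throughout, or that the primary outcome is biased in a known direction. The documents support neither. The problem touches only patients whose compliance runs through an unrecorded route, those whose new anticoagulation cannot be placed within 24 hours, and those whose food was withheld without an NBM order on admission. Unjustified NBM on admission, EN failure, and whether anticoagulation was started at all can be scored. Size, direction and effect on overall compliance cannot be derived. The conclusion assumes that data are collected as Section 5.5 lists them. It is a worthwhile, inexpensive correction, held with medium confidence.

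**What to change.** Add to Section 5.5, each with a not-documented code:

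- anticoagulation considered and withheld within 24 hours, reason documented: yes/no;
- date and time of first dose of new anticoagulation;
- EN offered: yes / declined / contraindicated / not needed, eating;
- light or normal diet given: yes/no, with date and time;
- reason for PN: EN failed / contraindicated / other.

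Score QPIs 9 and 11 from these fields.

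Where consideration or offer cannot be collected reliably from notes, reword QPI 9 and QPI 11 part 2 to count starting only, and exclude patients with a documented contraindication. That route still needs a contraindication item and the anticoagulation start time, and it leaves the diet and PN items to be added. If collection has closed, reword and report the unrecorded routes as a limitation.

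The cost is slightly more chart review per patient, using drop-downs like the QPI 6 item and date/time fields like those already used for opioids. Some offers and reasons will remain undocumented, and those patients should be shown as undetermined.
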